**Figure 1: Study Diagram**

d = day; DA = Basal insulin dose optimization; EOT = End of Treatment; ET = Early Termination; FU = follow-up; TC = telephone call; V = visit; W = week

Note: At weeks 11 and 25, subjects will attend a brief visit for application of a continuous glucose-monitoring sensor.

**Table 1: Study Procedures and Assessments**

Visit	1	2	3	4	TC	5	TC	--	6	TC	7	TC	8	TC	--	9 a	FU TC
Day or Week	Day -14 thru Day -1	Day 1	Week 2 $\pm$ 3d	Week 4 $\pm$ 3d	Week 6 $\pm$ 3d	Week 8 $\pm$ 3d	Week 10 $\pm$ 3d	Week 11	Week 12 $\pm$ 3d	Week 14 $\pm$ 3d	Week 16 $\pm$ 3d	Week 18 $\pm$ 3d	Week 20 $\pm$ 3d	Week 22 $\pm$ 3d	Week 25	Week 26 $\pm$ 3d	30 days $\pm$ 3d after Visit 9
Informed Consent	X																
Eligibility	X																
Medical History	X																
Randomization	X																
Concomitant Medicationsb	X	X	X	X	X	X	X		X	X	X	X	X	X		X	
Adverse Events	X	X	X	X	X	X	X		X	X	X	X	X	X		X	X j
Vital Signs	X	X	X	X		X			X		X		X				X
Height, Body Weight, BMIc	X	X	X	X		X			X		X		X			X	
Hematology & Chemistryd	X								X								X
Fasting Blood Glucose	X	X	X	X		X			X		X		X			X	
HbA1c	X					X					X					X	
Pre-dose Blood Sample for AIA	X								X								X
Optional Pre-dose PK Blood Sample for Insulin Glargine, M1, M2		X	X	X		X			X		X		X				X
UA, Pregnancy Teste	X	X	X	X		X			X		X		X				X
12-Lead ECG	X																X
Physical Examination	X																X
Glucometer and Supplies Issued, and Training	X																
Apply CGM Sensor and Issue Mealtime & Insulin Dose Recordf	X							X								X	
Collect CGM Sensor and Review Mealtime & Insulin Dose Record		X							X								X
IP and Other Supplies Issuedg		X	X	X		X			X		X		X				
Subject Training on IPh		X															
Review Insulin Use, Glucose Results, & Hypoglycemic Events Recordi		X	X	X	X	X	X		X	X	X	X	X	X		X	
Collect Used Insulin Kits			X	X		X			X		X		X			X	

AIA = anti-insulin antibody; BMI = body mass index; CGM = continuous glucose monitoring; d = Day; ECG = electrocardiogram; HbA1c = glycosylated hemoglobin; IP = investigational product; PK = pharmacokinetic; TC = telephone call; UA - urinalysis

a Any subject who withdraws from the study before Week 26 will perform all study activities scheduled for Visit 9 (EOT visit). Additionally, it is very important for site personnel to encourage subjects to visit the site at Week 26 ( $\pm$  4 weeks) (and Week 12  $\pm$  1 week if applicable) for a blood sample to be obtained for AIA and HbA1c measurements

b At screening, prior and concomitant medications will be collected. At every visit (except for visits to apply a CGM sensor) or telephone call, the Investigator or designee will inquire about concomitant medications, including insulin products taken before the first dose of IP.

c Height and body weight will be measured at the screening visit, and at subsequent visits, only body weight will be measured. The BMI will be calculated and recorded whenever the body weight is measured.

d Routine laboratory testing will include a complete blood count, a metabolic chemistry panel with serum lipids, and a thyroid stimulating hormone and free thyroxine.

e Women of childbearing potential will have a urine pregnancy test at screening and at each clinic visit.

f At the screening visit and at Weeks 11 and 25, subjects will attend a brief visit to have a CGM sensor applied. This visit should take place between 8 and 10 days before the scheduled visits at Weeks 12 and 26, respectively. Subjects will also be given a Mealtime & Insulin Dose Record to be completed during the 8-day CGM period that they will bring to the next visit.

g At these visits, subjects will be issued a supply of IP sufficient to last until the next clinic visit. They can also obtain more supplies for glucometer testing if needed.

h At Visit 2, the Investigator or designee will instruct the subject on all study procedures including proper IP administration.

i Subjects will bring the Hypoglycemic Events Record to each visit for review.

j Only serious adverse events to be queried.

Note: Following the screening visit, subjects will have their insulin dosing optimized as described in [Section 8.5.8](#).

## 8.2 Discussion of Study Design

This open-label study is designed to evaluate Gan & Lee Insulin Glargine Injection compared with that of Lantus® in subjects with type 1 diabetes to determine equivalence. Randomization will be stratified by country. Subjects will continue using their bolus insulin (which should not be changed for the duration of the study, with the exception of a dose change) and will substitute IP for their basal insulin.

## 8.3 Study Duration

Subjects will participate for 26 weeks. Recruitment will stop when approximately 275 subjects have been randomized to each treatment group. The study will end when the last subject completes the end-of-treatment visit, or discontinues the study treatment, whichever occurs first.

This study duration has been used in comparisons between other biosimilar long-acting insulin analogs and their reference products.

## 8.4 Study Population

The study population will be selected from subjects with type 1 diabetes who meet all the inclusion criteria and none of the exclusion criteria. Subject race and ethnicity will be collected according to FDA guidance [16].

### 8.4.1 Inclusion Criteria

Subjects must satisfy all of the following entry criteria before they will be allowed to participate in the study:

1. Male or nonpregnant, nonlactating female subjects between the ages of 18 and 75 years, inclusive
2. Ability to provide written, personally signed, and dated informed consent to participate in the study, in accordance with the ICH GCP Guideline E6 and all applicable regulations, before initiating any study-related procedures
3. Ability to understand and fully comply with all study procedures and restrictions.
4. Subjects with a confirmed diagnosis of type 1 diabetes mellitus who have been on an approved basal and bolus insulin regimen for at least 6 months (the type or brand of insulin should not have changed in the 6 months before screening)
5. HbA1c ≤ 11.0%
6. Body mass index (BMI) ≥ 19 kg/m^2 and ≤ 35 kg/m^2
7. Adherence to a prudent diet and exercise regimen recommended by the medical provider, and willingness to maintain these consistently for the duration of the study
8. Concomitant medications are allowed, provided that no significant dosing changes are anticipated during the study (see the exclusion criteria below and [Appendix 3](#) ([Section 17.3](#)) for specific allowed and prohibited concomitant medications); for

concomitant thyroid medications, subjects must have been on a stable dosage for 90 days before screening

#### 8.4.2 Exclusion Criteria

1. Participation in another clinical study or use of any study drug within 30 days before screening
2. Previous use of a biosimilar insulin, either basal or bolus
3. Diabetic ketoacidosis within a year before screening
4. Brittle type 1 diabetes mellitus within the year before screening (e.g., multiple hospitalizations related to diabetes mellitus and/or severe hypoglycemia for which the subject required 3rd party assistance)
5. Any severe, delayed sequela of diabetes mellitus, e.g., worsening end-stage renal disease, advanced coronary artery disease, or myocardial infarction within the year before screening, or autonomic peristaltic problems, e.g., gastroparesis
6. Anticipated change in insulin used during the study (change in dosage is allowed, but change in type or brand of insulin will result in the subject being withdrawn from the study)
7. Inadequately controlled thyroid disease, as reflected by a TSH value or free T4 > the upper limit of normal
8. BMI < 19 kg/m^2 or > 35 kg/m^2
9. Any clinically significant (in the opinion of the Investigator) hematology or chemistry test results at screening, including any liver function test > 3 × the upper limit of normal (subjects with elevated bilirubin due to Gilbert syndrome are eligible to participate)
10. Documented anti-insulin antibodies in the past
11. Treatment with glucocorticosteroids, immunosuppressants, or cytostatic agents within 60 days before screening (newly-prescribed or high-dose corticosteroids are prohibited; chronically administered oral, inhaled, topical, or intra-articular corticosteroids at a stable dosage are allowed if no increase in dose is anticipated during the study; see [Appendix 3](#) [[Section 17.3](#)] for a list of allowed and prohibited medications)
12. Current use of medication intended to cause weight loss or weight gain
13. Alcohol or substance use disorder within the 2 years before screening
14. Any previous or anticipated treatment with interferons
15. Any history of malignant disease within 5 years before screening, except for adequately treated basal cell carcinoma
16. Severe concomitant physical or psychiatric diseases or conditions
17. A history of a positive test result for HIV, hepatitis B, or hepatitis C; any subject who has a positive result during the study may continue at the discretion of the Investigator
18. Any history of pancreatitis or pancreatectomy

19. Any diagnosis or condition that requires the subject to undergo procedures that could decrease antibodies in plasma or that would require treatment with immunosuppressant agents
20. Any condition e.g., splenectomy, autoimmune disease, or rheumatologic disease, that could affect immunologic responses, could indicate an altered immune system, or could require treatment with a prohibited concomitant medication
21. Any unresolved infection or a history of active infection within 30 days before screening other than mild or viral illness (as judged by the Investigator)
22. Any other disease or condition that in the opinion of the Investigator could confound the study results or limit the subject's ability to participate in the study or comply with follow-up procedures; or any other factor that would indicate a significant risk of loss to follow up
23. Intolerance or history of hypersensitivity to insulin glargine or any excipient of IP
24. Inability or unwillingness to wear the CGM sensor as required for the study, or to comply with the concomitant medication requirements in the FreeStyle Libre Pro Indications and Important Safety Information, during the CGM periods

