#### **8.4.3 Withdrawal and Replacement of Subjects**

##### **8.4.3.1 Criteria for Subject Withdrawal**

In accordance with the Declaration of Helsinki ([Appendix 1, Section 17.1](#)) and other applicable regulations, a subject has the right to withdraw from the study at any time and for any reason without prejudice to his or her future medical care by the physician or at the institution.

Subjects may also be withdrawn from the study for any of the following reasons:

- The Investigator decides that the subject should be withdrawn. If this decision is made because of an intolerable adverse event or a clinically significant laboratory abnormality, the study medication is to be discontinued and appropriate treatment is to be provided. The Sponsor or designee is to be notified immediately.
- The subject requires a change in the type or brand of insulin (other than a change in dosage)
- The subject is unwilling to continue in the study
- Lack of compliance with protocol
- The Investigator or the Sponsor stops the study per [Section 15.8](#)
- The subject fails to respond to the study medication at an acceptable level, and the subject or Investigator determine another treatment is preferable.
- The subject fails to return to the clinic for scheduled visits and does not respond to telephone calls or written attempts at communication.

- If a subject becomes pregnant during the study, she will discontinue IP immediately, report the pregnancy to the Investigator, and attend an end-of-treatment visit. If the female partner of a male subject becomes pregnant, the subject may continue in the study, but the pregnancy should be reported. See [Section 11.7](#) of this document for more details about pregnancy reporting procedures.

The reason for withdrawal will be recorded in the clinical records and the electronic Case Report Form (eCRF). All subjects who are withdrawn from the study will attend an end-of-treatment clinic visit (see [Section 9.10](#)). All subjects who are withdrawn from the study should be offered appropriate follow-up medical care.

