### 9.11 Early Termination Visit

For any subject who is withdrawn before completing all study visits, the Investigator will ensure that the following steps are taken at an early termination (ET) visit:

- Conduct an ET visit performing study activities listed under Visit 9 ([Section 9.10](#)) no later than 14 days after withdrawal or discontinuation from the study
- If the subject fails to attend a scheduled ET visit, site staff will make at least 2 attempts to contact the subject via telephone and 2 attempts via written communications delivered by courier (delivery should be confirmed and documented). If the subject does not respond to any of these attempts at communication, he or she will be considered lost to follow-up
- Complete all appropriate eCRF pages, providing the date of and explanation for the subject's withdrawal/discontinuation
- When indicated, the Investigator should arrange for appropriate follow-up medical care for the subjects

**If a subject discontinues the study prematurely, it is very important for site personnel to encourage subjects to visit the site at Week 26 ( $\pm$  4 weeks) (and Week 12  $\pm$  1 week, if applicable) for a blood sample to be obtained for AIA and HbA1c measurements.**

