### 10.4 Electrocardiogram

Computerized 12-lead ECG recordings will be obtained, after the subject has been supine for 5 minutes. Each lead will be recorded for at least 3-5 beats at a speed of 25 mm/sec paper speed and 10 mm/mV amplitude. At a minimum, heart rate, P, PR, QRS, QT and corrected

QT intervals (msec) will be recorded from the 12-lead ECG. A copy of all ECGs will be retained on site and these may be collected for central review if required (i.e., in case emerging ECG data necessitate expert evaluation).

For the purposes of screening, the Investigator or a designee will evaluate whether the ECG is normal or abnormal, and if abnormal, whether the abnormality will exclude the subject from participating in the study.

Investigators may repeat ECGs for quality or safety reasons. Any abnormal finding deemed to be clinically relevant by the Investigator will be reported as an adverse event. Subjects with clinically relevant cardiovascular side effects or adverse events, or clinically relevant ECG changes must be withdrawn from the study (see [Section 8.4.3](#)).

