## 12.7 Primary Endpoint

### 12.7.1 Incidence of Treatment-Induced Anti-Insulin Antibodies

The primary analysis for immunogenicity will be an equivalence test using the TOST approach with  $\alpha=0.05$  which is algebraically equivalent to comparing the limits of the 90% confidence interval (CI) for treatment-induced AIA development via a test of difference in proportions based on normal approximation (-margin, +margin) where the margin is dependent on the observed treatment-induced AIA rate in Lantus® and is defined in [Table 4](#). The estimand of interest for the primary immunogenicity analysis is the difference in treatment-induced immunogenicity rates regardless if all subjects tolerate or adhere to study treatment or receive other insulin treatments. Intercurrent events will be handled according to the treatment policy strategy. Treatment Policy strategy is defined as the strategy that considers “The occurrence of the intercurrent event is irrelevant: the value for the variable of interest is used regardless of whether or not the intercurrent event occurs” (See ICH E9 R1 addendum [\[17\]](#)).

Sensitivity analyses including worst-case imputation and using a ‘Composite Strategy’ will be conducted.

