5.1 Sample Size and Power

Enrollment was planned for 550 subjects overall (275 subjects per treatment group). The primary analysis for the immunogenicity primary endpoint was to be an equivalence test for the difference in proportion of subjects who develop treatment-induced AIAAs between Gan & Lee insulin Glargine Injection and Lantus® using the 2 Wald one-sided tests (TOST) with $\alpha=0.05$ (Chow and Shao 2002 (1)). After scientific and regulatory review, the method to evaluate immunogenicity equivalence will be the 90% confidence intervals of risk difference from the logistic regression analysis (see Section 3.1). Under this newly adopted approach, no power loss is expected.

This sample size of 275 subjects per treatment group was chosen to achieve over 80% power using the TOST equivalence test for two proportions, a risk difference of zero and equivalence margins dependent on the observed treatment-induced AIA rate per Table 3 below. For example, a total sample size of 550 will provide approximately 85% power for the TOST equivalence test using a treatment-induced AIA rate of 30% and a margin of 12% (Table 3). The treatment-induced AIA is defined as newly confirmed positive AIA development or important (at least a 4-fold) increase in AIA titers, after baseline and up to visit Week 26 (see the definition of Primary Endpoint in Section 6.1 and Section 7.2). No drop outs are considered in the calculation. A larger than expected early discontinuation rate was observed as part of study monitoring activities and therefore protocol amendment 3 approved on 25-Apr-2019 included procedures to encourage subjects to return for assessments even if they had discontinued treatment early.

The appropriate similarity margin, based on the actual observed event rate for the intended reference product, will be used for final analysis after database lock as summarized in Table 3 below. The power calculation in the table was adapted for a sample size of 550 using the treatment-induced AIA rate for the reference product. Linear interpolation will be used for values between AIA rates in the table.

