11.6.1 Primary Endpoint

11.6.1.1 Incidence of Treatment-Induced Anti-Insulin Antibodies

Incidence of treatment-induced AIA is defined as subjects develop newly confirmed positive AIA or have important (4-fold) increase in AIA titer up to visit Week 26. The objective of the primary immunogenicity analysis will be to evaluate equivalence of Gan & Lee Insulin Glargine Injection to Lantus® by comparing the limits of the 90% confidence interval (CI) of country-adjusted difference in proportions of treatment-induced AIA development to the specified margins (-margin, +margin) where the margin is dependent on the unadjusted treatment-induced AIA rate in Lantus® and is defined in Section 5.1, Table 3.

The estimand of interest is the country-adjusted difference in treatment-induced AIA rates regardless if all subjects tolerate or adhere to study treatment or receive other insulin treatments. Intercurrent events will be handled according to the treatment policy strategy. Treatment Policy strategy is defined as the strategy that considers "The occurrence of the intercurrent event is irrelevant: the value for the variable of interest is used regardless of whether or not the intercurrent event occurs" (See ICH E9 R1 addendum). All AIA data collected, scheduled and unscheduled, will be considered for the analysis, even if collected after the occurrence of intercurrent events of (1) discontinuing study treatment, (2) returning to initial treatment and/or (3) initiating a new treatment.

Any treatment-induced AIA after baseline and up to visit Week 26 will have the subject count as treatment-induced AIA for the primary endpoint. The visit window (defined in Section 7.1) will only be limited to include assessment within 210 days from the first dose.

Missing data will be handled as described in Section 11.6.1.2. The SS will be used for the primary analysis.

The number and percentage of subjects in each treatment group who develop treatment-induced AIA as defined in Section 7.2 after baseline and up to visit Week 26 (upper limit of the visit window) will be evaluated using a logistic regression model adjusted by country (CNTRY) estimating the country-adjusted difference in proportions along with the corresponding 90% confidence interval (CI).

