11.7.2 Secondary Efficacy Endpoints

11.7.2.1 Proportion of Subjects Achieving Glycemic Control

The following secondary efficacy variables will be analyzed using the 90% CI of differences in proportions:

- The number and percentage of subjects who achieve an FBG test result of ≤ 6.0 mmol/L (≤ 108.0 mg/dL) at visit Week 26
- The number and percentage of subjects who achieve a HbA1c of $< 7.0\%$ at visit Week 26.

The difference in proportions will be estimated along with the corresponding 90% CI in the FAS using a logistic regression model. Subjects without values available at week 26 will be considered as having not achieved glycemic control. Samples from subjects who have discontinued study but returned to provide assessment for Week 26 will be included for this analysis.

Additionally, number and percentages of subjects who achieve an FBG test result of ≤ 6.0 mmol/L (≤ 108.0 mg/dL) and number and percentages of subjects who achieve a HbA1c of $< 7.0\%$ will be presented by time point and treatment group.

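### The withdrawal rules can end study assessments at events after which the treatment-policy estimands still need data; later sampling is only encouraged and omits FBG

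*Protocol*

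**What the plan says.** **Conduct rules.** Protocol 8.4.2, exclusion 6: a "change in type or brand of insulin will result in the subject being withdrawn from the study". Protocol 8.4.3.1 lists the same event, together with inadequate response and non-compliance, under a permissive opening: "Subjects may also be withdrawn from the study for any of the following reasons". Protocol 10.4 is mandatory again: subjects with "clinically relevant ECG changes must be withdrawn from the study", with a cross-reference to 8.4.3.

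**Estimands.** Protocol 12.7.1 defines the primary contrast "regardless if all subjects tolerate or adhere to study treatment or receive other insulin treatments". SAP 11.6.1.1 uses all AIA data, "even if collected after the occurrence of intercurrent events of (1) discontinuing study treatment, (2) returning to initial treatment and/or (3) initiating a new treatment". Protocol 12.8.1 applies the treatment-policy strategy to HbA1c as well.

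**Follow-up after exit.** Protocol 9.11 requires an early termination visit with the Visit 9 procedures within 14 days. After that, sites are asked to encourage a return at Week 26 ± 4 weeks (and Week 12 ± 1 week if applicable) "for a blood sample to be obtained for AIA and HbA1c measurements". FBG is not on that list.

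**Missing data and size.** Protocol Table 5 counts a subject with a missing Week 12 or Week 26 AIA result as having treatment-induced AIA. The main HbA1c analysis in SAP 11.7.1 imputes missing Week 26 values, within arm, from subjects who stopped treatment early and came back. Protocol 12.2 makes no allowance for dropout. SAP 5.1 reports: "A larger than expected early discontinuation rate was observed as part of study monitoring activities".

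**FBG endpoint.** SAP 11.7.2.1 counts a missing Week 26 value as failure and states: "Samples from subjects who have discontinued study but returned to provide assessment for Week 26 will be included for this analysis".

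**The concern.** The same event is treated in two ways. In the conduct rules, a switch of insulin is a reason to leave the study. In the estimand it is irrelevant, and the outcome after it is still wanted. A site that follows exclusion 6 or 10.4 closes the subject out, and later sampling then depends on the subject's goodwill. SAP 7.3 also blurs the distinction: it identifies adverse events leading to discontinuation of IP by a CRF question about discontinuation from the study.

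Exits for changed insulin or inadequate response are likely to be related to outcome, and in an open-label trial they may differ by arm. At stake are a primary comparison that rests partly on positive imputation, and an HbA1c analysis whose imputation model is built on the subjects who chose to return.

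**Working it through.** **Inputs.** 275 per arm, one-sided α = 0.05 per test, a 30% AIA rate, a 12-point margin and a true difference of zero (protocol 12.2, SAP 5.1); margins by linear interpolation in protocol Table 4; missing counted as positive (protocol Table 5). Assumed, because the documents give no rates: the missingness in each arm, and that it is unrelated to true AIA status.

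**Step 1: reproduce the plan's figure.** With unpooled variance, SE = √(2 × 0.3 × 0.7 / 275) = 0.0391. Power = 2Φ(0.12/0.0391 − 1.645) − 1 = 84.6%, against about 85% stated. The formula can be used.

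**Step 2: imputation model.** If a fraction m is missing and scored positive, a true rate p becomes p + (1 − p)m. With difference d and margin M, the chance of declaring equivalence is Φ((M − d)/SE − 1.645) − Φ((−M − d)/SE + 1.645).

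**Step 3: equal loss, no true difference.** At 10% per arm, both rates become 0.30 + 0.70 × 0.10 = 0.37. The margin moves to 12.5 + 0.3 × 2/5 = 12.62 points, and power is 84.4%. Across 5–20% equal loss it stays at 84–85%, because the margin widens as the imputed Lantus rate rises.

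**Step 4: unequal loss, no true difference.**
- 10% test, 5% reference: rates 0.370 and 0.335, d = 3.5 points, M = 12.0 + 0.5 × 3.5/5 = 12.35 points, SE = 0.0407. Power = Φ(0.529) − Φ(−2.248) = 68.9%.
- 15% test, 5% reference: rates 0.405 and 0.335, d = 7.0 points, same margin. Power = 36.5%.

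**Step 5: equal loss, true difference at the margin (42% v 30%).**
- None missing: 5.0%.
- 10% per arm: rates 0.42 + 0.58 × 0.10 = 0.478 and 0.370. The difference shrinks to 10.8 points while the margin grows to 12.62. SE = 0.0419, and the chance of declaring equivalence is Φ(−1.210) = 11.3%.
- 20% per arm: rates 0.536 and 0.440, d = 9.6 points, M = 12.96 points; 19.7%.

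Simulation of 400,000 trials per scenario, with the margin taken from each trial's observed Lantus rate, gives 68.5% and 36.9% for Step 4, and 5.8%, 11.9% and 19.8% for Step 5.

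**Step 6: FBG.** The return visit collects AIA and HbA1c only. SAP 11.7.2.1 covers FBG ≤ 6.0 mmol/L and HbA1c < 7.0% with one sentence about returners. That sentence works for HbA1c. For FBG the listed procedures supply no sample, so a returner with no other usable value is scored as a failure.

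**The case against.** The strongest reply is that the plan foresees these exits. The early termination visit draws AIA, HbA1c and FBG; retrieval is sought at Weeks 12 and 26; data after the event are used up to day 210. There are composite, per-protocol and completer analyses for AIA, and multiple imputation, MMRM and tipping-point analyses for HbA1c. Equal loss does not reduce primary power (Step 3). All of this stands. A reader might infer that the objectives cannot tolerate the missing data, and the documents do not support that. However, sensitivity analyses test assumptions and do not replace observed values. SAP 11.7.1.3 itself allows that, for the per-protocol set, returners may be too few to support the imputation.

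Other stronger readings also fail:
- **Sites must always withdraw a subject who changes insulin.** Exclusion 6 reads that way, but 8.4.3.1 is permissive. The finding is an unresolved contradiction.
- **Returners cannot have a Week 26 FBG.** A late early termination visit may supply one for some subjects. They are simply not scheduled for one at the return visit.
- **Adverse-event follow-up is cut short by withdrawal.** Serious events are collected for 30 days after the last dose, and the treatment-emergent window also ends 30 days after it. Completers' non-serious events also stop at the last visit, so this is not specific to withdrawal.
- **Total early discontinuation measures the defect.** It includes withdrawn consent and loss to follow-up, which these rules do not cause.

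**Conclusion.** The point holds in limited form. Exclusion 6, 8.4.3.1 and 10.4 disagree on whether withdrawal is mandatory, and all three speak of leaving the study, while both main estimands need outcomes after such events. With later sampling only encouraged and no dropout allowance, the rules can generate missing data that the analysis then fills by rule or by model.

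The size of the effect in this trial is unknown: the SAP gives no discontinuation rate, and neither document attributes exits to these rules. The illustrations in Steps 4 and 5 show two risks. Unequal loss against the test arm costs power, and equal loss scored as positive biases toward equivalence. They rest on a 30% true rate, missingness unrelated to AIA status, the positive-imputation rule of protocol Table 5 (SAP Table 4 is only partly legible in the available text), and an unadjusted Wald interval in place of the SAP's country-adjusted one.

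**What to change.** - Reconcile protocol 8.4.2 (exclusion 6, also in the synopsis), 8.4.3.1 and 10.4 with each other and with the estimands, without changing any rule on when IP stops. The insulin-change wording is not limited to basal insulin, so replacement text that ordered IP to stop would reach a bolus brand switch; none is proposed.
- State that these events do not end study assessments: the subject is asked to keep the remaining scheduled assessments, at least the Week 12 and Week 26 samples, unless consent is withdrawn or the subject is lost to follow-up.
- Add FBG to the return-visit samples in protocol 8.1, 9.11 and Table 1 footnote a.
- Report, by arm, withdrawals by reason and AIA and HbA1c retrieval rates.

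The cost is some visits for subjects off IP and a protocol amendment with ethics approval; under protocol 15.2, altered procedures may also require a revised consent form and repeat consent. The synopsis expected the study to end in 2019 and the SAP is dated 27 May 2021. If follow-up is complete, the reporting item is what can still be done.
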